--------------	--

	
achieve a non-dilated pupil diameter of at least 5 mm, they will be excluded from the study. If a subject meets a 5 mm pupil on most time points of both sets of lenses, but not all, inclusion of data acquired smaller than 5 mm will be scaled to 5 mm and considered on an individual basis.
 
Equipment:
 
 1. An aberrometer (e.g. COAS-HD, CSO Osiris) will be used for all optical measures. The aberration data will be obtained for central 3- and 5-mm diameter areas. Wavefront data will be reconstructed by both modal (up to 6th order Zernike polynomials) and zonal (local slope) methods.
Sample size	Complete N=21, enroll up to N=24
Hypothesis	
 1. The Air Optix plus Hydraglyde lens will have levels of variation in aberration throughout the day not significantly different than the naked eye. 2. The Air Optix Aqua lens will have levels of variation in aberration throughout the day not significantly different than the naked eye. 3. The Air Optix plus Hydraglyde lens will have lower variation in aberration throughout the day relative to the Air Optix Aqua lenses.
TEST COMPARATOR PRODUCTS	
Baseline = Naked eye
 
Lenses: Set of soft lenses
 
 1. Air Optix plus Hydraglyde on daily disposable basis 2. Air Optix Aqua on daily disposable basis (ALCON will provide lenses)
INCLUSION/EXCLUSION CRITERIA	
 1. Habitual prescription within the range of +5.00 D to -6.00 D 2. 18-35 years of age 3. No history of issues of eye alignment or binocularity by self-report 4. No doctor diagnosed, self-reported accommodative or binocular vision issues 5. No doctor diagnosed, self-reported ocular surface disease or dry eye requiring regular, ongoing treatment 6. The subject must appear able and willing to adhere to the instructions set forth in this clinical protocol. 7. Vertex corrected refractive cylinder must be -0.75 or less. 8. Visual acuity best correctable to 20/25 or better for each eye 9. The subject must read and sign the Informed Consent form. 10. No active conditions that may prevent soft contact lens wear. 11. Mesopic pupil size >5.00 mm.
OFF LABEL	No.

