No pharmacological dilation will be used in this study. Subjects will be in a dark room aiming to achieve a natural pupil diameter of at least 5 mm. Upon inclusion, if a subject cannot achieve a non-dilated pupil diameter of at least 5 mm, they will be excluded from the study. If a subject meets a 5 mm pupil on most time points/lenses, but not all, inclusion of data acquired smaller than 5 mm will be scaled to 5 mm and considered on an individual basis.

Equipment:

1. An aberrometer (e.g. COAS-HD or CSO Osiris) will be used for all optical measures. The aberration data will be obtained for central 3- and 5-mm diameter areas. Wavefront data will be reconstructed by both modal (up to 6th order Zernike polynomials) and zonal (local slope) methods.
2. A Medmont corneal topographer will be used following each set of aberration measures to also monitor the tear film upon the eye/contact lens.

SUBJECTSSample Size:

This section describes the rationale and approach used to establish the minimum sample size (N) needed to achieve 80% power at a nominal significance level $\alpha=0.05$ for detecting a mean difference between percentage change in RMS of higher-order wavefront aberrations measured over a 12-hr period for the test lenses and the percentage change observed without a contact lens (no-CL). For each subject and lens, a series of five RMS measurements will be obtained at 0 hours (baseline) and at six, 2-hr intervals within each period. Technically, the statistical power for testing the contact lens main effect will depend not only on the structure of the covariance matrix but also on how the baseline measurements recorded at time=0 hours are incorporated into the statistical model(s). But, given the degree of uncertainty about the input parameter values required to estimate sample size, we believe it reasonable to base initial calculations on a dependent sample t-test on a mean difference score under the assumption of no differential carryover effect. Thus, the target parameter of interest for our primary analysis corresponds to the true difference in the mean post-baseline percentage change over 12 hours between each of the test contact lenses and no-CL for N subjects. Note that this test would be equivalent to testing the interaction of "lens" and "hours of use" factors in a two-way repeated measurements ANOVA.

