where μ is the overall mean, α_i is the effect for the i^{th} sequence, $\rho_{j(i)}$ is the random effect for the j^{th} individual within the i^{th} sequence (i.e. $\rho_{j(i)} \sim N(0, \sigma_\rho^2)$), γ_k is the effect of the k^{th} period, τ_l is the effect of the l^{th} lens effect and λ_m is the effect of the m^{th} carryover effect with e_{ijkl} being the NIID residual term (i.e., $e_{ijkl} \sim N(0, \sigma_e^2)$). Assuming that there is no statistical evidence of a period x lens interaction ($\gamma\tau_{kl}$), we will use a one-sided equivalence (i.e., non-inferiority) test to determine whether the average percentage increase in higher-order RMS induced by Dailies1 Lens is no worse than the average increase without a contact lens. In practice we can use a single directional paired-sample t-test to test the null hypotheses. If we reject H_0 we should conclude that the percentage increase over a 12-hour period in higher-order RMS induced by each of the test lenses is no worse than the increase measured without a contact lens. In this context, smaller differences in the mean difference in higher-order RMS are “better.” Thus, the statistical hypotheses are arranged so that rejecting the null hypothesis for the specified null difference implies that, the observed mean change over 12 hours for each of the test lenses is not significantly worse than the mean change with no-CL. i.e.,

$$H_0: \mu_D - \mu_{NC} \geq M_{IN} \text{ versus } H_a: \mu_D - \mu_{NC} < M_{IN}$$

Interpretation of non-inferiority test of the Dallies Total1 (test) to the reference non-contact lens (active control). Shaded area represents the non-inferiority range. Hypotheses are arranged so that larger mean difference values lead to rejection of the null hypothesis. ■ = observed point estimate of mean difference; both A and C show 1-sided confidence intervals; B and D show 2-sided CIs. Both A and E imply that Dallies Total1 is non-inferior to active non-contact lens control because the entire CI is below non-inferiority margin (3.25%). C and D imply the Dallies is inferior although a larger sample is needed to shrink the CI so that the entire interval C falls in the region of inferiority.

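### The formal non-inferiority hypothesis names a lens that is not in the trial, and its single rejection is worded as a conclusion about both study lenses

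*Combined protocol and SAP*

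**What the plan says.** - **Statistical Analysis.** After the carryover model, the question put is whether "the average percentage increase in higher-order RMS induced by Dailies1 Lens is no worse than the average increase without a contact lens". One symbolic pair is given for it: H0: μ_D − μ_NC ≥ M_IN against Ha: μ_D − μ_NC < M_IN. The type of test is fixed by "we will use a one-sided equivalence (i.e., non-inferiority) test", and the mechanics by "In practice we can use a single directional paired-sample t-test to test the null hypotheses". Rejection is then worded as a finding of non-inferiority for both products: "we should conclude that the percentage increase over a 12-hour period in higher-order RMS induced by each of the test lenses" (the sentence goes on to set this against no lens). The figure legend reads its confidence-interval cases for Dailies Total1 and puts the margin at 3.25%.
- **Protocol Synopsis (Test Comparator Products) and Lenses.** The study products are Air Optix plus Hydraglyde and "Air Optix Aqua on daily disposable basis", with the naked eye as baseline. No Dailies lens is listed.
- **Subjects, Sample Size.** Dailies Total1 appears because no data existed on the two test lenses. The null difference is 3.5% (an observed 2% plus 1.5%). The target parameter is "the true difference in the mean post-baseline percentage change over 12 hours between each of the test contact lenses and no-CL".
- **Outcome Measures, Primary.** Each Air Optix lens is compared with no lens, independently of the other.
- **Protocol Synopsis, Hypothesis.** Items 1 and 2, one per lens, predict no significant difference in variation from the naked eye. Item 3 predicts lower variation with Hydraglyde than with Aqua.

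**The concern.** The section that defines the primary test should say which product is tested, against what margin, and what follows from the result. Here the product is wrong and the margin is a symbol whose only number in that section disagrees with the sample-size section. The conclusion also moves from one rejected null to two lenses. Rejection for one lens carries no evidence about the other, and the text does not say what is concluded if one passes and the other fails. Since two lenses are compared with the same reference, a mixed result is an ordinary possibility. With the rule unclear, the choice of what to claim could be made after the results are known.

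**Working it through.** **Step 1. Which lens, which test, which conclusion.**

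| Place | Lens | Form of the statement |
|---|---|---|
| Synopsis, Hypothesis 1 and 2 | each Air Optix lens | no significant difference from naked eye; no margin |
| Outcome Measures, Primary | each Air Optix lens, separately | comparison of means with no lens; no margin |
| Sample Size | each test lens | paired t-test, null difference 3.5% |
| Statistical Analysis, H0/Ha | Dailies (μ_D) | non-inferiority, margin M_IN |
| Statistical Analysis, conclusion | each of the test lenses | non-inferiority |
| Statistical Analysis, legend | Dailies Total1 | non-inferiority, margin 3.25% |

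The only row with a formal hypothesis pair concerns a product that yields no data in this trial. The Synopsis does not fill the gap. Failing to find a significant difference is not the same as showing that the difference lies below a margin, and a small or noisy trial can do the first without the second.

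**Step 2. Reproduce the stated power.** Inputs from Sample Size and Table 1: N = 21, mean difference 2.75, null difference 3.5, SD 2.1 per condition, correlation 0.80, α = 0.05 one-sided.

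- SD of the paired difference = 2.1 × √(2 × (1 − 0.80)) = 1.328
- δ = √21 × (3.5 − 2.75) / 1.328 = 2.59, with 20 degrees of freedom
- Power (noncentral t) = 0.8034; Table 1(b), index 12, gives 0.803

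All 15 rows of Table 1(b) reproduce in this way. So 0.80 is right for one lens against no lens at the 3.5% null difference.

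**Step 3. What the legend's margin would do.** With 3.25 in place of 3.5 and everything else unchanged:

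- δ = √21 × (3.25 − 2.75) / 1.328 = 1.73
- Power = 0.509 per lens

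The power depends on the distance between the true difference and the margin. Here that is 0.50, the same as 3.50 − 3.00 in index 15 of Table 1(b), where the plan's own N is 46.

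**Step 4. Power if a claim for both lenses were wanted.** This needs the correlation between the two lens-minus-no-lens differences, which the documents do not give. If all three conditions share one SD (σ) and one correlation ρ, the covariance of the two differences is σ²(1 − ρ) and each variance is 2σ²(1 − ρ), so they correlate 0.5. Simulating the two paired t-tests at N = 21, with both true differences at 2.75 and a margin of 3.5:

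| Correlation of the two differences | Both tests reject |
|---|---|
| 0 | 0.646 |
| 0.25 | 0.666 |
| 0.5 | 0.690 |
| 0.75 | 0.723 |
| 0.9 | 0.752 |
| 1 | 0.803 |

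The result also depends on the assumed true difference. At correlation 0.5 it is 0.92 if both lenses are at 2.50 and 0.999 if both are at 2.00. With 24 completers and both at 2.75 it is 0.757.

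**The case against.** The strongest reply is that the intention is plain. The primary outcome section names the right lenses and compares them independently, the Synopsis has one worded hypothesis per lens, and the Statistical Analysis section itself refers once to null hypotheses in the plural. On that reading the H0/Ha line is a template, carried over from a Dailies plan and meant to be applied once per lens, and the correction is editorial. Much of this stands: the intended comparisons can be recovered and the design is not affected. It does not remove the point, because the non-inferiority rule is set out only in this section, and there it has the wrong product and no settled margin.

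Two stronger readings are tempting, and the documents do not support them.

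- *The trial has power 0.69 instead of 0.80.* The plan sets its power per lens, that figure reproduces, and nothing says that both lenses must succeed. The 0.69 requires a both-lens claim, both true differences at 2.75 and an assumed correlation of 0.5.
- *The plan would make a false claim about the second lens in about 80% of trials.* That follows if one lens is at 2.75, the other exactly at the margin, and a rejection for either is carried to both. The plan states no such rule, and the independent comparisons in the primary outcome section argue against it.

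**Conclusion.** The point holds as a defect in the definition of the primary test. The one formal hypothesis is written for a lens outside the trial, its single rejection is worded as covering both study lenses, and this does not match the two separate comparisons planned elsewhere. It should be corrected before analysis because it is the operative decision rule.

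The stated power is not in error: 0.803 per lens at N = 21 is correct for a true difference of 2.75 and a null difference of 3.5%. What could change it is the margin conflict, since 3.25% would bring per-lens power to about 0.51 under the same inputs. Joint power of 0.65 to 0.80 matters only if the sponsor wants a claim for both lenses, and it rests on an assumed range of 0 to 1 for the correlation between the two differences.

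**What to change.** In the Statistical Analysis section:

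1. Remove the Dailies references from the text and the legend, and state two hypotheses. H01: μ(Air Optix plus Hydraglyde) − μ(no lens) ≥ M_IN. H02: μ(Air Optix Aqua) − μ(no lens) ≥ M_IN. Each alternative is that the difference is below M_IN.
2. State that the conclusion for each lens rests only on its own test, so that a mixed result has a defined reading.
3. Give M_IN one numerical value and use it in the sample-size section, the hypotheses and the legend. The 3.5% and 3.25% must be reconciled.
4. Reword Synopsis hypotheses 1 and 2 as non-inferiority within that margin.
5. Optionally, say in the sample-size section that 0.80 is per lens and, if a both-lens claim is wanted, report its power as a range (about 0.65 to 0.80 at N = 21 with both differences at 2.75) with the correlation assumption stated.

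If 3.5% is kept, the cost is wording only, with no extra subjects. If 3.25% is kept, the sample-size section has to be redone.

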Data was not available on the two test lenses, so we used previously published data on an ALCON lens expected to provide similar responses. Specifically, we approximated parameter values for [1] effect size, [2] within-subject variance, and [3] within-subject correlation from the data reported in two previous studies. Specifically, Montes-Mico, *et al* (2013) measured wavefront aberrations in 15 myopic eyes before and at 2-hr intervals after contact lens fitting over a 12-hr period. Using the 5-mm pupil diameter data presented in Figure 2 of the referenced paper, we estimated that the group-averaged percentage change between the baseline (i.e., 2-hr after lens fitting) and the final measurement (i.e., after 12-hr wearing time) of ~3% and ~5% for no-CL and DAILIES TOTAL ONE (DT1) lens, respectively. Note that this difference between no-CL and DT1 was smaller than any of the other lenses under test, but mirrors the expectation for the current test lenses. To allow for mean differences larger than the observed 2% mean difference between each of the test lenses and no-CL in the current study, we added a 1.5% non-inferiority margin; thus, our sample size calculation assumes a 'null difference' of 3.5%.

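### Rejecting the non-inferiority null shows only that a lens is worse than no lens by less than the margin, but the plan reports it as no worse and words Hypotheses 1 and 2 as no significant difference

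*Combined protocol and SAP*

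**What the plan says.** The Statistical Analysis section specifies a one-sided non-inferiority test by paired t-test, with H0: μ_D − μ_NC ≥ M_IN against Ha: μ_D − μ_NC < M_IN. It then prescribes what rejection means, in two forms. The first is that the 12-hour percentage increase "in higher-order RMS induced by each of the test lenses is no worse than the increase measured without a contact lens". The second, tied to the specified null difference, is that "the observed mean change over 12 hours for each of the test lenses is not significantly worse than the mean change with no-CL".

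The figure caption in the same section uses a different and correct criterion: a result is non-inferior "because the entire CI is below non-inferiority margin (3.25" percent).

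In the synopsis, Hypotheses 1 and 2 each state that the named lens "will have levels of variation in aberration throughout the day not significantly different than the naked eye".

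The Sample Size section takes 12-hour changes "of ~3% and ~5% for no-CL and DAILIES TOTAL ONE (DT1) lens, respectively" as its guide, adds 1.5% to the 2% difference, and concludes that "our sample size calculation assumes a 'null difference' of 3.5" percent. M_IN is given no number where the hypotheses are written.

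**The concern.** A one-sided test at a positive margin answers one question: is the excess smaller than the margin? It does not ask whether the excess is zero. *Not significantly worse* and *not significantly different* are statements about a test at zero, and the plan commits to no such lens versus no-lens test. It also commits to no confidence interval for that difference, from which a reader could see whether zero is excluded. Hypotheses 1 and 2 are non-directional and carry no margin, so the planned test cannot establish them.

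The wording matters more here than it often would. The null difference of 3.5 points is larger than the whole expected no-lens change (about 3%) and already contains the expected 2-point worsening. Every true difference in Table 1(b) lies between 2.00 and 3.00, so the trial is sized on the assumption that the lens is worse. A lens with a clear, statistically significant extra increase could then be presented as no worse than the naked eye, and this is the primary conclusion of a study intended for presentation.

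**Working it through.** **Inputs.** From the Sample Size section: SD 2.1% per condition; r = 0.70, 0.75, 0.80; α = 0.05; null difference 3.5 points; expected difference 5 − 3 = 2 points. N = 21 completers. From the caption: alternative margin 3.25.

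**Reproducing the plan.** SD_diff = 2.1 × √(2(1 − r)). For r = 0.80 this is 2.1 × √0.40 = 1.328. With true difference 2.75, the noncentrality parameter is √21 × (2.75 − 3.5)/1.328 = −2.59, and the one-sided 0.05 noncentral t power is 0.803, as in row 12 of Table 1(b). The same method reproduces all 15 rows. A two-sided 0.05 test does not (row 12 would need 27 pairs). The planned test is therefore one-sided against 3.5.

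**Results that pass and are also significantly worse than no lens.** SE = SD_diff/√21. With SD_diff at its planned value:
- significantly worse than zero (two-sided 0.05) if the observed difference exceeds t(0.975, 20) × SE = 2.086 × SE;
- H0 rejected if the observed difference is below M_IN − t(0.95, 20) × SE = M_IN − 1.725 × SE.

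| r | SD_diff | SE | Lower edge | Upper edge, M_IN 3.5 | Upper edge, M_IN 3.25 |
|---|---|---|---|---|---|
| 0.70 | 1.627 | 0.355 | 0.740 | 2.888 | 2.638 |
| 0.75 | 1.485 | 0.324 | 0.676 | 2.941 | 2.691 |
| 0.80 | 1.328 | 0.290 | 0.605 | 3.000 | 2.750 |

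Any observed difference between the edges meets the success rule and contradicts *not significantly worse*. Near the top of the range at r = 0.80, a 3% no-lens change would go with almost 6% with the lens.

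**How often, at the plan's expected excess of 2.0.** By noncentral t, for r = 0.70, 0.75, 0.80:
- P(pass), M_IN 3.5: 0.9925, 0.9976, 0.9996;
- P(pass), M_IN 3.25: 0.9603, 0.9811, 0.9941;
- P(significantly worse): 0.99965, 0.99995, 0.999998.

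Simulating the mean and sample SD (2,000,000 draws per case) gives P(significantly worse | pass) of at least 0.9996 for every r. At the 2.75 design point it is essentially 1.

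**Sensitivity.** M_IN 3.5, ranges over r = 0.70 to 0.80. SDs other than 2.1% are assumptions.

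| True excess | SD | P(significantly worse given pass) |
|---|---|---|
| 1.0 | 2.1% | 0.76–0.91 |
| 0.5 | 2.1% | 0.27–0.38 |
| 0 | 2.1% | 0.025 |
| 2.0 | 4.2% | 0.64–0.88 |
| 2.0 | 6% | 0.10–0.38 |

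In the last two rows, P(pass and significantly worse) over all trials is 0.42–0.71 and 0.04–0.20. With M_IN 3.25 the conditional figures are 0.57–0.86 and 0.06–0.29.

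**The case against.** The test itself is set up correctly. The section names it as non-inferiority, writes the margin into H0, ties the conclusion to the specified null difference, and reads the interval properly in the caption. *No worse* is common shorthand for non-inferiority; taken alone it would be a minor wording point. The decision rule, type I error and power are untouched, so this could be treated as a reporting clarification. Any positive margin with enough precision allows a result that is non-inferior yet significantly worse, so much of the size above comes from how the margin was built. The near-certain frequencies also rest on the SD of 2.1%. That figure comes from √(4.41 × 10⁻⁴) = 0.021 µm, which is 2.1% only if mean RMS is 1 µm; the documents give no mean RMS. At an assumed SD of 8.4%, both events occur together in only about 0.1–1% of trials. Finally, the Sample Size section speaks of detecting a mean difference, and descriptive summaries are promised, so an excess would be partly visible.

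The point about SD stands: the frequencies are conditional on the plan's inputs. The rest does not remove the problem. *Not significantly worse* is not shorthand for non-inferiority; it is a different claim, and the section says that rejection implies it. The correct caption does not override that instruction or the synopsis hypotheses, and it carries a different margin. The phrase about detecting a difference is sizing rationale, not a committed analysis, and descriptive summaries are not an interval for the paired difference.

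**Conclusion.** The concern holds and should be corrected before analysis. Whatever the SD, the correlation or the true difference, rejecting H0 at a positive M_IN does not support *not significantly worse*, does not support an unqualified *no worse*, and does not test Hypotheses 1 and 2 as written. Under the plan's own inputs the conflict is the normal outcome: at a true excess of 2.0 points and SD 2.1%, more than 99% of trials pass at a margin of 3.5, and at least 99.9% of those are also significantly worse than no lens. If the true excess is near zero or the SD is much larger than planned, the conflict is less frequent, but the prescribed conclusion still goes beyond the test.

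**What to change.** 1. State one value of M_IN beside the hypotheses, reconciling the 3.5% of the Sample Size section with the 3.25% of the caption. Make clear that the 1.5% is a component of the 3.5% and not the margin tested.
2. Reword Hypotheses 1 and 2 and the success statement along these lines: the mean 12-hour percentage increase in higher-order RMS with the lens exceeds that without a lens by less than M_IN percentage points. Remove *no worse* and *not significantly worse*.
3. For each lens, commit to reporting the two-sided 95% CI for lens minus no lens, and to saying so when it excludes zero on the worse side.

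The one-sided wording matches the planned test. If similarity in both directions is what Hypotheses 1 and 2 intend, a two-sided equivalence test is the alternative, but that changes the analysis and its power would have to be worked out.

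The cost is text in the synopsis and the statistical section, plus one interval per lens from the same paired data. Sample size, test and data collection do not change. The downside is a less favourable claim. This corrects only the conclusion; whether a margin that includes the expected 2-point worsening is acceptable is a separate question.

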Our within-subject variability and correlation estimates were taken from Cheng, *et al* (2004) who reported on the stability of clinical monochromatic aberrometry measurements over a wide range of time scales. First, temporal variability of wavefront root mean square (RMS) error, excluding defocus and astigmatism, was tracked across five repeated measurements for 4 subjects at four different time scales. The averaged variance estimates for different time scales ranged from $8.10 \times 10^{-5} \mu\text{m}^2$ ($t < 1$ second) to $9.73 \times 10^{-4} \mu\text{m}^2$ ($t < 1$ year). For our calculations, we used their reported value of $4.41 \times 10^{-4} \mu\text{m}^2$ ($t < 1$ week) as our variance estimate, which translates to a standard deviation of 2.1%. We expect that this is a worst-case scenario because the value was derived by calculating the between-day variances for individual trials across five days for each subject and then calculating the average across the four subjects and five trials on each day. Our data will be multiple measurements taken within a 12-hr period on the same day. Second, Cheng, *et al* (2004) reported a within-subject correlation estimate of $r=0.799$ that was based on a linear regression analysis of the higher-order RMS error measurements over a one-year time scale for subject AB. Again, because the time-scale in the current study proposal is only 12 hours (i.e., is much shorter than 1 year), we expect that the magnitude of the within-subject correlation in our sample is likely to be 0.80 higher. For purposes of the sample size calculation, we used three values for the correlation parameter, i.e., $r = \{0.70, 0.75, \text{ and } 0.80\}$. The input parameters for this sample size calculation scenario are shown in Table 1(a). The actual power and number of paired observations for this scenario are presented in Table 1(b) and were obtained using SAS 9.4 by varying both the mean difference and the correlation parameters.

Table 1 (a)

Fixed Scenario	
Distribution	Normal
Method	Exact
Number of Null	L
Alpha	3.50 %
Standard	0.05
Nominal	2.10 %
	0.80

Table 1 (b)

Index	Mean Diff	Corr	Actual Power	N Pairs
1	2.00	0.70	0.810	9
2		0.75	0.822	8
3		0.80	0.838	7
4	2.25	0.70	0.802	12
5		0.75	0.829	11
6		0.80	0.824	9
7	2.50	0.70	0.804	18
8		0.75	0.822	16
9		0.80	0.819	13
10	2.75	0.70	0.806	31
11		0.75	0.805	26
12		0.80	0.803	21
13	3.00	0.70	0.801	67
14		0.75	0.801	56
15		0.80	0.808	46

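### The primary non-inferiority test has no single margin, its interpretation text reverses the rejection direction, and its conclusion claims more than rejection can show

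*Combined protocol and SAP*

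**What the plan says.** **Margin.** Statistical Analysis states H0: μ_D − μ_NC ≥ M_IN against Ha: μ_D − μ_NC < M_IN, with no number for M_IN. The sentence that introduces the hypotheses says that "rejecting the null hypothesis for the specified null difference implies that" the lens is acceptable, again without a number. The only number in that section is in the text that explains the confidence-interval figure: non-inferiority is shown "because the entire CI is below non-inferiority margin (3.25"%). The Sample Size section takes an expected difference of 2% and says "we added a 1.5% non-inferiority margin; thus, our sample size calculation assumes a 'null difference' of 3.5"%. Table 1(a) also prints 3.50%.

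**Direction.** The interpretation text says "Hypotheses are arranged so that larger mean difference values lead to rejection of the null hypothesis". Ha, the sentence that smaller differences are better, and the requirement that the whole interval lie below the margin all point the other way.

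**Conclusion.** On rejecting H0, the plan concludes that the percentage increase "induced by each of the test lenses is no worse than the increase measured without a contact lens". It then says that "the observed mean change over 12 hours for each of the test lenses is not significantly worse than the mean change with no-CL". Hypotheses 1 and 2 in the Protocol Synopsis expect no significant difference from the naked eye.

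**Lens name.** The sentence that introduces the test refers to the increase "induced by Dailies1 Lens is no worse than the average increase without a contact lens". The interpretation text also names a Dailies lens. The two lenses in this trial are Air Optix plus Hydraglyde and Air Optix Aqua.

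**The concern.** This test gives the primary verdict for both lenses, so its threshold, rejection region and conclusion should each be fixed before the data are seen. The threshold is not fixed: an analyst who uses the one number printed in the analysis section applies a margin for which the trial was not sized. An observed difference between two of the printed margins' cut-offs passes under one and fails under the other, so the verdict could be chosen afterwards.

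The conclusion wording is a separate problem and remains whichever margin is chosen. The plan itself expects a lens about 2 points worse than no lens. A test against a margin above 2 is designed to pass such a lens. To report that result as no worse, or not significantly worse, contradicts data that may show a clear difference from zero.

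**Working it through.** **Inputs.** One-sided α = 0.05, paired t-test (Sample Size; Statistical Analysis). SD 2.1% and r = 0.70, 0.75 or 0.80 (Sample Size, Table 1). Expected difference 5% − 3% = 2%; null difference 2% + 1.5% = 3.5%. Target N = 21.

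**Formulas.** SD of the paired difference: σ_d = 2.1 × √(2(1 − r)), which is 1.627, 1.485 and 1.328 for r = 0.70, 0.75 and 0.80. Noncentrality: δ = √N × (true difference − M_IN)/σ_d. H0 is rejected when t falls below −t(0.95, N − 1). Power comes from the noncentral t distribution.

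**Step 1: reproduce Table 1(b).** With M_IN = 3.5% and lower-tail rejection, N and power match in 15 of 15 rows. Row 12 (difference 2.75, r = 0.80): δ = √21 × (2.75 − 3.5)/1.328 = −2.59, power 0.803, N = 21. With 3.25% no row matches: row 1 needs 12 pairs, not 9, and row 12 needs 46, not 21. With 1.5% no row can apply, because every tabulated difference (2.00 to 3.00) is above it. The table therefore fixes both the 3.5% and the lower-tail direction. Upper-tail rejection at a true difference of 2.75 would have power below 0.1% with either 3.5% or 3.25%.

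**Step 2: effect of the margin at N = 21.** Half-width = 1.725 × σ_d/√21 = 0.612, 0.559 and 0.500. The largest observed difference that passes is M_IN minus the half-width.

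| M_IN | Largest passing difference, r = 0.80 | P(pass), true 2.0, r = 0.70 to 0.80 | P(pass), true 2.75, r = 0.80 |
|---|---|---|---|
| 3.5% | 3.00 | 99.2% to >99.9% | 80.3% |
| 3.25% | 2.75 | 96.0% to 99.4% | 50.9% |
| 1.5% | 1.00 | about 0.1% or less | practically 0 |

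An observed difference of 2.9 passes at 3.5% and fails at 3.25%. At a true difference of 2.0, verdicts under 3.5% and 3.25% differ in 0.6% to 3.2% of trials.

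**Step 3: what passing shows.** A lens is significantly above zero (one-sided 0.05) when the observed difference exceeds the half-width, and it passes at 3.5% when the difference is below 3.5 minus the half-width. Both hold for observed differences of 0.50 to 3.00 (r = 0.80) or 0.61 to 2.89 (r = 0.70). At a true difference of 2.0, 99.2% to >99.9% of trials fall in that range. For an observed 2.9 at r = 0.80, the two-sided 95% interval is 2.9 ± 2.086 × 0.290, or 2.30 to 3.50: wholly above zero, yet declared no worse.

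**Step 4: dependence on the SD.** The Sample Size section takes a variance of 4.41 × 10⁻⁴ µm², "which translates to a standard deviation of 2.1"%. That is an SD of 0.021 µm, which equals 2.1% only if baseline RMS is 1 µm. The documents give no baseline RMS, so two larger values are assumed here: SD 4.2% (baseline 0.50 µm) and SD 6.0% (baseline 0.35 µm). True difference 2.0, r = 0.70 to 0.80:

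| SD | Passes at 3.5% and significantly above zero | Verdict differs, 3.5% v 3.25% |
|---|---|---|
| 2.1% | 99.2% to >99.9% | 0.6% to 3.2% |
| 4.2% (assumed) | 51% to 76% | 13.2% to 13.6% |
| 6.0% (assumed) | 9% to 30% | 9.0% to 11.6% |

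If a two-sided 95% interval is used to judge the difference from zero, the middle column becomes 42% to 71% at 4.2% and 4% to 21% at 6.0%. It is practically unchanged at 2.1%.

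**The case against.** The margin can largely be recovered. Statistical Analysis refers to the specified null difference, the term that the Sample Size section attaches to 3.5%, and Table 1(a) prints the same value. The 3.25% occurs once, in text that explains a figure and names a lens not in this trial, so it is probably carried over. The 1.5% is an increment with a loose label, and nobody is likely to use it as the threshold. The formal hypotheses have a coherent direction; only one sentence is reversed. Any non-inferiority test with a positive margin can pass a treatment that is significantly worse than control. At the plan's expected difference and SD, 3.5% and 3.25% seldom give different verdicts, and the fall to 50.9% power applies at a true difference of 2.75.

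Most of this stands, and it narrows the point. The live conflict is 3.5% against 3.25%, and the direction error would mislead only a reader who trusted the interpretation text over Ha. But recovering 3.5% takes inference from another section, and the only number the analysis section prints contradicts it. That passing is compatible with being worse is the reason the conclusion must carry the margin; the plan's conclusion sentence omits it, and the next sentence denies significant worsening, which the test does not examine.

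**Conclusion.** The concern holds on all three parts. The analysis section leaves M_IN without a number and prints a margin, 3.25%, that did not produce N = 21; at the row that did, power under it is 50.9% rather than 80.3%. The direction sentence contradicts Ha. The conclusion wording matters most: with the plan's own SD of 2.1%, N = 21 and a true difference of 2 points, over 99% of trials would report a lens as no worse when the data show it significantly worse than no lens. That share rests on the 2.1% SD. It falls to 51% to 76% at an assumed 4.2% and to 9% to 30% at an assumed 6.0%, but the wording is unsupported at any SD. All figures assume normally distributed paired differences and one-sided α = 0.05. The point should be corrected before analysis.

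**What to change.** - Give M_IN one number in H0/Ha and repeat it in the interpretation text. 3.5% is the value behind N = 21. State in Sample Size that the 1.5% is an increment added to the expected 2% and is not M_IN.
- If 3.25% is intended, restate the power: at SD 2.1%, r = 0.80 and N = 21 it reaches 80% only for true differences up to 2.50, and a true difference of 2.75 needs 46 pairs.
- Change the direction sentence to say that smaller mean differences lead to rejection.
- Word the success conclusion, and Hypotheses 1 and 2, as less than M_IN percentage points worse than no lens. Report the confidence interval beside it so that a difference above zero is visible.
- Replace the Dailies wording in the test sentence and interpretation text with text for the two Air Optix lenses.

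The cost is protocol and SAP wording only. Visits, data and N stay as they are if 3.5% is kept; another margin also requires a new power statement.
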